## 7.3. Every two cycles ( $\pm 7$ days)

- Disease assessment will be performed every 2 cycles starting at cycle 3 (cycle 3, 5, 7, etc.) for the first 19 cycles (18 months):
  - o CT/MRI chest, abdomen, pelvis (±7 days).
  - o Whole body bone scan if positive for mets at screening or if clinically indicated.

- o If bone lesion detected from whole body bone scan, repeat bone scan, bone X-ray, CT, or MRI of the largest skeletal lesion identified.
- o If skin lesion detected by physical exam at screening, skin color photography.
- Subjects will be assessed every 2 cycles starting after cycle 5 (cycle 7, 9, 11, etc.):
  - o Physical exam, weight
  - o Vital signs
  - o ECOG performance status
  - o Blood chemistries (sodium, potassium, serum creatinine calcium, albumin, ALT, AST, bilirubin, alkaline phosphatase)
  - o Platelets, ANC and hemoglobin
  - Pregnancy test for women of childbearing potential (WOCP), if clinically indicated. If the urine test is positive or cannot be confirmed as negative, a serum pregnancy test will be required.
  - o Assess adverse events
  - Concomitant medications
  - o Dispense 2 cycles of Palbociclib
  - o Prescribe Tamoxifen (commercial supply)

# 7.4. Every three cycles ( $\pm 7$ days)

- Disease assessment will be performed every 3 cycles starting at cycle 22 (cycle 22, 25, etc.) until discontinuation of study drug:
  - o CT/MRI chest, abdomen, pelvis (±7 days).
  - o Whole body bone scan if positive for mets at screening or if clinically indicated.
  - o If bone lesion detected from whole body bone scan, repeat bone scan, bone X-ray, CT, or MRI of the largest skeletal lesion identified.
  - o If skin lesion detected by physical exam at screening, skin color photography.
- Correlative blood sample: day 1 of every 3rd cycle starting at cycle 8 (cycle 8, 11, etc.)

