# **Subjects Who Do Not Begin Study Treatment**

If subject signs consent, is registered to the study, and later is not able to begin the planned study treatment, for whatever reason, the subject will be removed from study and treated at the physician's discretion. The subject will be considered a screen/baseline failure and be replaced. The reason for removal from study will be clearly indicated in EDC system.

If a subject begins treatment, and then is discontinued for whatever reason, the subject must be followed per section 7.5.

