# 7. STUDY CALENDAR & EVALUATIONS

[Cycle = 28 days]							T		
	Scree	ening	Cycle 1	Cycle 2	Cycle 3-5	Every 2 cycles	Every 3 cycles	Safety follow up	Long-Term follow up
Study Day	-28 days	-14 days	Day 1 	Day 1 (±3)	Day 1 (±3)	(± 7)	(± 7)	30 days (±7) post last study drug	Every 3 months (±14) for 2 years from registration
REQUIRED ASSESSMENTS									
Informed Consent/ HIPAA auth.	X								
Medical hx including prior therapies; pathology	X								
Physical examination	X		X	X	X	C7+		X	
Vital Signs, weight, height (screen only)	X		X	X	X	C7+		X	
ECOG status	X		X	X	X	C7+		X	
Baseline signs/ symptoms; AE assessment	X		X	X	X	C7+		$X^5$	
Concomitant medications	X		X	X	X	C7+		X	
Survival									$X^6$
LABORATORY TESTS									
Blood Chemistries 		X	X	X	X	C7+			
Platelets, ANC & Hgb 		X	D1, D15	D1, D15	X	C7+			
Pregnancy test for WOCP 		-72h	X	X	X	C7+			
DISEASE ASSESSMENT 						C3-19	C22+		
CT/MRI chest, abdomen/pelvis	X					$X^8$	$X^8$		X
CT or MRI Brain, if clinically indicated	X								
Whole body bone scan	X					$X^{8,9}$	$X^{8,9}$		
Bone x-ray, CT, or MRI 	X					$X^8$	$X^8$		
Skin color photography, if applicable	X					$X^8$	$X^8$		
TREATMENT EXPOSURE									
Palbociclib (Day 1-21)			X	X	$X^{16}$	$C7+^{16}$			
Tamoxifen (Continuous)			х —		—	C7+			
CORRELATIVE STUDIES (SPECIMEN COI	LLECTI	ION)					C8, 11, etc.		
Tumor tissue (unstained slides) 			X					$X^{11}$	
Blood for circulating tumor DNA 			X		C5		$X^{12}$	$X^{12}$	
BANKING SAMPLES (SPECIMEN COLLECTION)									
Whole Blood 			X						
Unstained Slides  (archival, if available)			X						
Serum and Plasma 			X					X	

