#### Footnotes:

- 1: For cycle 1 only: labs do not need to be repeated if done within 7 days of day 1.
- 2: Blood Chemistries to include: sodium, potassium, serum creatinine (or GFR; see 3.1.8), calcium, albumin, ALT, AST, bilirubin, alkaline phosphatase.
- 3: For Cycles 1 and 2 only, hematology assessments done on Day 1 and also on Day 15
- 4: A negative serum or urine pregnancy test is required within 72 hours of study registration and at the beginning of each cycle, if clinically indicated. If the urine test cannot be confirmed as negative, a serum pregnancy test will be required.
- 5: For subjects with unresolved treatment-related toxicity, follow as medically appropriate until resolution or stabilization
- 6: Survival assessment to be recorded every 3 months until 2 years from registration
- 7: Appropriate scans to assess disease status will be obtained within 28 days of study enrollment including CT chest, abdomen/pelvis. PET/CT: The CT portion of PET/CT is usually of lower quality and should typically not be used in place of dedicated diagnostic CT. However, if the CT portion is of diagnostic quality, it may be used.
- 8: Disease assessment will be performed on Day 1 of every 2 cycles starting at cycle 3 (ex. Day 1 of cycle 3, 5, 7, etc.) for the first 19 cycles (18 months). Disease assessment will be performed on Day 1 of every three cycles starting at cycle 22 (ex. Day 1 of cycle 22, 25, etc.) until discontinuation of study drug.
- 9: Bone scan will be repeated as per footnote 8 above only if positive for bone mets at the time of screening or if clinically indicated.
- 10: If bone lesion(s) detected from whole body bone scan, perform bone x-ray, CT or MRI of the largest bone metastatic area.
- 11: Histological confirmation of breast cancer diagnosis is required (Section 3.1.3). Although not required as a protocol procedure, a patient with a new metastatic lesion should be considered for biopsy whenever possible to reassess ER/PR/HER2 status, if clinically indicated. Also, biopsy at the time of progression should be considered as clinically indicated, but it is not required as a protocol procedure. If a biopsy is prospectively done as standard of care, the study would like to collect samples for correlative research. Unstained slides from either the fresh biopsy or from an archival tumor specimen (metastatic lesion) may be submitted at baseline.

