# 7.7. Long Term Follow-up Evaluations (±14 days)

Subjects will continue to be followed for survival every 3 months for 24 months after registration.

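### The calendar schedules CT/MRI after study drug stops but the text does not, and the 24-month follow-up has two starting points, so it is unclear whether progression after an unprogressed stop is looked for

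*Combined protocol and SAP*

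**What the plan says.** **Imaging after drug stops.** Section 7.4 states "Disease assessment will be performed every 3 cycles starting at cycle 22 (cycle 22, 25, etc.) until discontinuation of study drug", and calendar footnote 8 repeats it: "starting at cycle 22 (ex. Day 1 of cycle 22, 25, etc.) until discontinuation of study drug". Section 7.3, for cycles 3 to 19, gives no stopping point, but its visits are tied to treatment cycles. Sections 7.5 and 7.6 list no imaging. Section 7.7 reads "Subjects will continue to be followed for survival every 3 months for 24 months after registration" and mentions no scans.

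The calendar differs. Its long-term column is headed "Every 3 months (±14) for 2 years from registration", and the row "CT/MRI chest, abdomen/pelvis" carries a mark there, without footnote 8. It is the only disease-assessment row so marked. Section 8.3 also asks for objective progression to be sought after treatment ends, but only for symptomatic deterioration.

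**The clock.** Sections 5.1 and 7.5.1 count 24 months from discontinuation. The calendar header, section 7.7 and footnote 6 ("Survival assessment to be recorded every 3 months until 2 years from registration") count from registration.

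**The endpoint.** Section 8.4.6 counts the first documented progression or death from any cause, with no restriction to time on drug, and censors non-progressors at the last disease evaluation. Section 7.5.1 allows drug to stop without progression (toxicity, subject request, physician judgement, pregnancy). Section 5.5 prohibits nothing in post-treatment follow-up, and 8.4.6 does not say how new therapy before progression is treated.

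**The concern.** PFS is the primary endpoint, in a single arm read against a fixed 15-month null. No control arm shares an error in how progression is ascertained.

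Take a subject who stops drug without progression. A site working from the text may take no further scans and censor at the last on-drug scan. A site working from the calendar scans three-monthly to month 24. The same history then gives different PFS data, and both practices may be mixed among 48 subjects. If those who stop have a different prognosis from those who stay on drug, the first practice is informative censoring. Even if they do not, it loses events.

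**Working it through.** **1. The plan's own figure.** Inputs from 12.3: medians 15 and 25 months, one-sided 0.05, power 80%, exponential test, accrual 24 months, follow-up 24 months (taken as 24 further months), 20% allowance.

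- Events: (1.645 + 0.842)² / ln(25/15)² = 23.7.
- P(event) at median 25, with λ = ln2/25: 1 − (e^(−24λ) − e^(−48λ))/(24λ) = 0.6246.
- 23.69/0.6246 = 37.9, so 38 subjects; 38/0.8 = 47.5, so 48.

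The stated N reproduces. Nothing below changes it.

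**2. Bias if scans end at drug stop.** None of these inputs is in the documents. Assume on-drug hazard λ, stopping hazard μ with μ/(λ+μ) = 10%, 20% or 30%, and hazard θλ after stopping. Nothing is recovered after the stop. With a = λ+μ and b = θλ, true PFS is

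S(t) = e^(−at) + μ(e^(−bt) − e^(−at))/(a − b).

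λ is chosen so that S(15) = 0.5. Censoring at the stop estimates the on-drug hazard alone, so the apparent median is ln2/λ. Example, θ = 2 and 20% stopping: λ = 0.04343, μ = 0.01086, S(15) = 0.4429 + 0.0571 = 0.500, apparent median 0.6931/0.04343 = 15.96.

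The error column is the simulated one-sided error of the exponential test in 12.3 at a true median of 15 (Wald test on the log hazard, uniform accrual, cutoff month 48, range over n = 38 and 48). With no stops it is 3.9% and 4.3%.

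| θ | Apparent median at 10/20/30% stopping | Error |
|---|---|---|
| 0.67 | 14.80 / 14.55 / 14.25 | 2–3% |
| 1 | 15.00 / 15.00 / 15.00 | 4% |
| 2 | 15.45 / 15.96 / 16.56 | 6–12% |
| 3 | 15.73 / 16.58 / 17.56 | 7–19% |

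**3. Same model with the calendar scans**, off-drug progression seen to month 24 whatever therapy follows: median 14.98–15.03, error 3.7–4.7% in every cell. If 25% of subjects (assumed) are bone-only and unseen off drug, the median is 14.81–15.47 and the error 3.8–6.1%.

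**4. Events lost without bias.** Here θ = 1, median 25, 38 evaluable, and 10/20/30% have stopped unprogressed by month 24 (a different parameter from step 2).

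| Off-drug scans | Events | Power |
|---|---|---|
| To data cutoff | 23.7 | 80% |
| To 24 months after stop | 23.5 / 23.2 / 23.0 | 80 / 79 / 79% |
| To 24 months from registration | 22.8 / 22.0 / 21.2 | 79 / 77 / 76% |
| None | 21.7 / 19.6 / 17.6 | 77 / 73 / 69% |

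If all 48 subjects contribute until they stop, the last row becomes 27.4 / 24.8 / 22.2 events and 85 / 82 / 78% power. The 20% allowance therefore absorbs part of the loss, provided it is not used up elsewhere.

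**5. The clock.** At median 25, e^(−0.02773 × 24) = 51% are progression-free at month 24. Anyone stopping after that has no follow-up left on the registration clock and 24 months on the other. If off-drug deaths are counted but scans are not (θ = 2, post-progression median survival of 12 or 36 months assumed), the choice of clock moves median PFS by at most 0.3 months.

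**The case against.** **The passages can be read in sequence.** Section 7.4 and footnote 8 may end only the cycle-based schedule, with the calendar's three-monthly scans following; the long-term mark carries no footnote 8. This stands as a possible reading. It leaves 7.7 silent on imaging and 7.4 without that limit, so a site can reasonably reach either answer.

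**The section 4 pointer is probably stale.** It says a treated subject who is "discontinued for whatever reason, the subject must be followed per section 7.5". The index still lists 7.5 as safety follow-up, so the pointer seems to predate renumbering. It is a cross-reference to correct, not evidence of a rule against imaging.

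**Nothing excludes a late progression from PFS.** A reader might infer that the passage followed decides whether such a progression counts. It does not: 8.4.6 would count any that is documented. What varies is whether anyone looks.

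**The clock is mostly a survival matter.** This is right. Sections 7.5.1, 7.7 and footnote 6 word it for survival. It reaches PFS only through the length of off-drug scanning and the capture of deaths.

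**The size is assumed, and modest at moderate θ.** Also right. At θ = 2 the shift is about 0.5 to 1.6 months, against a design difference of 10. Section 12.4 plans estimation and names no test, so the median shift matters more than the error rates.

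**Conclusion.** Both inconsistencies are in the current text and should be reconciled. Finding them needs no assumption; their effect on PFS does.

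It is tempting to conclude that PFS will be overstated. The documents do not support that. They give no expected rate of unprogressed stops and no mix of reasons, and the direction depends on θ: no bias at 1, PFS too long above 1, too short below 1. Over 10–30% stopping and θ from 0.67 to 3, a true median of 15 months reads as 14.3 to 17.6 when scans end at drug stop, and about 15.0 when the calendar is followed to month 24. At θ = 1 the cost is events only: power 77–69% instead of 80% with 38 evaluable subjects, partly covered by the 20% allowance. Nor do the inconsistencies make the sample size wrong: N = 48 reproduces.

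Confidence is high on the text and medium on materiality.

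**What to change.** - **7.7:** state that subjects who stop drug without progression keep the CT/MRI already marked in the calendar until progression, death or the end of the calendar's follow-up. In 7.4 and footnote 8, say that discontinuation ends only the cycle-based schedule.
- **Clock:** use one starting point in 5.1, 7.5.1, 7.7, the calendar and footnote 6.
- **Section 4:** correct the cross-reference.
- **8.4.6:** state how new anti-cancer therapy before progression is handled.
- **12.4 (optional):** a sensitivity analysis counting new therapy or symptomatic deterioration as an event. Label it a deliberately low bound. With the calendar scans in place and half of stops counted, it gives about 13.2–14.5 months at θ = 2 against a true 15, so it and the primary estimate should not be presented as bracketing the truth.
- **Stated limit:** the bone and skin rows have no long-term mark, so off-drug progression in bone-only subjects may still be missed.

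The cost is amendment wording and, at sites that had followed the text, off-drug scans the calendar already schedules. At the assumed 10–30% stopping, about 3–12 of 48 subjects stop before month 24, giving about 11–48 scans in total on the registration clock (θ of 1 to 2). Choosing the discontinuation clock for imaging would add to that.

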#### 7.5. Off Treatment

# 7.5.1. Protocol therapy discontinuation

A subject will be discontinued from the protocol therapy under the following circumstances:

- If there is evidence of disease progression
- If the treating physician thinks a change of therapy would be in the best interest of the subject
- If the subject requests to discontinue protocol therapy
- If the protocol therapy exhibits unacceptable toxicity
- If a female subject becomes pregnant

Subjects can stop study participation at any time. However, if they decide to stop, subjects will continue to be followed for survival for 24 months after discontinuation.

## 7.6. Safety Follow-up Evaluations

Subjects discontinued from the treatment phase of the study for any reason will be evaluated within 30 days ( $\pm$  7) of the last dose of study drug.

- Physical exam, weight
- Vital signs
- ECOG performance status
- Assess adverse events
- Concomitant medications
- Correlative blood samples at the time of progression
- Optional standard biopsy at the time of progression, with extra passes for research.
- Banking samples. See Correlative Laboratory Manual for specific instructions.

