#### **Prohibited Concomitant Medications**

Subjects are prohibited from receiving the following therapies during the Screening and Treatment Phase of this trial:

- Anti-cancer systemic chemotherapy or biological therapy not specified in this protocol
- Other investigational and antineoplastic therapies

Subjects who, in the assessment by the investigator, require the use of any of the aforementioned treatments for clinical management should be removed from the trial.

There are no prohibited therapies during the Post-Treatment Follow-up Phase.

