- 12: Blood for circulating tumor DNA will be collected cycle 1 day 1, cycle 5 day 1 and day 1 of every subsequent 3rd cycle (e.g. cycle 8, 11, etc.), and at time of progression.
- 13: Submission of whole blood for banking is to be collected at Pre-Treatment Cycle 1 Day 1. See CLM for collection, processing, labeling and shipping instructions.
- 14: Submission of unstained slides for banking from an archived FFPE tumor block (if available). See CLM for collection, labeling, and shipping instructions.
- 15: Submission of serum and plasma for banking are to be collected at Pre-Treatment Cycle 1 Day 1 and at the 30 Day Safety Follow up visit. See CLM for collection, labeling, processing, and shipping instructions.
- 16: After cycle 5, subjects will be assessed every 2 cycles (cycle 7, 9, 11, etc.). Two cycles of palbociclib may be dispensed from cycle 5 onward.

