To compare the protein contents of exosomes, total exosome will be first extracted from each plasma sample as previously described (27, 28). Once separated, the exosome from each sample will be labeled with Tandem Mass Tag (TMT) isobaric tags for quantitative mass spectrometry (MS) analysis. Exosomes obtained from each patient prior to treatment will be measured three times in three independent experiments as technical replicates. To improve the detection and quantitation of low abundant exosome proteins, we will use existing exosome proteomics data and ExoCarta (http://www.exocarta.org/) to guide our analysis. Specifically, an inclusion list will be generated to include all the known exosome proteinderived peptides, as well as proteins that belong to candidate resistance mechanisms (e.g. Cdk2, cyclin E, Rb, and other cell cycle regulatory proteins and proteins involved in ER signaling). We will also guide the mass spectrometer to aim for these ions as specific retention time points. This type of experiment is similar to multiple reaction monitoring (MRM), which is highly sensitive and reproducible. After mass spectrometry analysis, all the data will be analyzed and quantified using ProLuCID (29) and Census (30) to generate a complete exosome protein identification and quantitation data set. We will then analyze the data to identify key proteins and pathways that contribute to the differences between responders and non-responders in pre-treatment samples. This will provide insight into possible mechanisms of primary resistance. For the responders, we will also compare the exosome proteome at baseline vs. at the time of progression. This will provide insight into potential mechanisms responsible for secondary (i.e. acquired) resistance to CDK 4/6i. For both analyses, we will, in addition, correlate with the primary outcome PFS.

Protein clusters that persistently change together will be subject to pathway analysis using STRING database (http://www.string-db.org/). With both the proteomics data and transcriptomics data, we will perform a multi-omics data integration to find the correlation between the proteome and the transcriptome. We have previously shown that such analysis could greatly improve the quality and confidence of the results (26).

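### The progression blood sample is timed in two ways, and section 9.1 does not set aside samples drawn after another anti-cancer regimen has begun

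*Combined protocol and SAP*

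**What the plan says.** **Where the draw is placed.** In the calendar (section 7), the row headed "Blood for circulating tumor DNA" has its only post-treatment mark in the safety follow-up column, timed "30 days (±7) post last study drug". The calendar has no progression or end-of-treatment column. Section 7.6 lists "Correlative blood samples at the time of progression" among the procedures of that visit, but words the visit's timing more loosely: "Subjects discontinued from the treatment phase of the study for any reason will be evaluated within 30 days" (±7) of the last dose.

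**How the draw is described.** Footnote 12, attached to the calendar mark, begins "Blood for circulating tumor DNA will be collected cycle 1 day 1, cycle 5 day 1 and day 1 of every subsequent" third cycle, and ends "and at time of progression". Section 9 also places the third exosome sample at progression, after Cycle 1 Day 1 and Cycle 5 Day 1. It describes these samples in the past tense, as already collected.

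**How the sample is used.** For responders, section 9.1 states "we will also compare the exosome proteome at baseline vs. at the time of progression", and presents the difference as insight into acquired resistance to CDK4/6 inhibition.

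**What may happen in between.** Progression ends protocol therapy (section 7.5.1). The part of section 5.5 on prohibited medications then says: "There are no prohibited therapies during the Post-Treatment Follow-up Phase".

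**The concern.** A site that follows the calendar can draw the sample labelled as progression several weeks after progression was documented and with a different regimen under way, and still be compliant. Section 9 prefers exosomes to circulating tumor DNA because their cargo shows which pathways are currently active. A readout chosen for that reason can be expected to respond to whatever drug the subject is taking when blood is drawn. The targeted list in 9.1 includes cell-cycle regulators and proteins of ER signaling as examples of candidate resistance mechanisms, and a next-line regimen could plausibly act on either.

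Section 9.1 has no rule to exclude, flag or separate samples drawn after new therapy. In a paired comparison of baseline with progression, an effect of the next regimen would look the same as a resistance mechanism. What is at stake is the interpretation of one correlative analysis, not the trial's efficacy or safety conclusions.

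**Working it through.** The plan states no figure on this point, so the check is date arithmetic on the plan's own windows.

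**Inputs**
- Cycle of 28 days, palbociclib on days 1–21, tamoxifen daily (section 5.3.1).
- Scheduled scans on Day 1 of a cycle (calendar footnote 8).
- Safety visit at 30 ± 7 days after last study drug (calendar), or within 30 days (±7) of the last dose (section 7.6).
- Concomitant medications recorded to 30 days after the last dose, and after that only for SAEs (section 5.5).

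**Step 1. Window for the draw.** Calendar: 30 − 7 = 23 to 30 + 7 = 37 days after last study drug. Section 7.6 read literally: about 0 to 37 days. Footnote 12: the time of progression, with no reference to the last dose.

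**Step 2. Delay after a scheduled progression scan.** Count from Day 1 of the previous cycle, so that the scan falls on day 29.
- If palbociclib (day 21) is the last study drug: 21 + 23 = 44 to 21 + 37 = 58. The visit is 44 − 29 = 15 to 58 − 29 = 29 days after the scan.
- If tamoxifen, stopped on day 28, is the last study drug: 28 + 23 = 51 to 28 + 37 = 65. The visit is 51 − 29 = 22 to 65 − 29 = 36 days after the scan.

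**Step 3. Time off palbociclib.**
- Draw on the day of the scan: 29 − 21 = 8 days, with tamoxifen continuing to the day before or the day itself.
- Draw at the safety visit: 23 to 37 days if palbociclib was last, or 51 − 21 = 30 to 65 − 21 = 44 days if tamoxifen was last.
- The baseline draw (Cycle 1 Day 1) is before any study drug.

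Both candidate draw times at a scheduled progression are therefore off palbociclib, as is baseline. The two times differ in the length of the gap, in tamoxifen exposure, and in whether a new regimen may have begun.

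**Step 4. Can new therapy start before the draw?** Section 5.5 does not prevent it. Section 11.4.1 expects that it may: SAE reporting runs to 90 days after the last dose or to the start of a new anti-cancer treatment, whichever is first. A 15- to 36-day gap lies well inside that period. No section requires the blood to be drawn before the next regimen.

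**Step 5. Could affected samples be identified?** Largely. Concomitant medications are recorded to day 30 and are listed again at the safety visit. The calendar window runs to day 37, so days 31–37 fall outside the general recording rule. Section 9 does not say that these data will be used.

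**Step 6. Scale of the comparison.** The documents give no response rate for this combination. If the 25–30% that section 1.1 cites for first-line tamoxifen is taken as an assumption, responders number 0.25 × 48 = 12 to 0.30 × 48 = 14.4. Each affected pair would then be about 1/14 = 7% to 1/12 = 8% of the comparison, if every responder progresses and is sampled. A higher response rate gives more pairs; missing samples give fewer. How many pairs are affected is not in the documents.

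**The case against.** The strongest defence is that the plan does mean the sample to be drawn at progression. Section 7.6, footnote 12 and section 9 all say so. Footnote 15 names the 30-day visit explicitly for banked serum and plasma, so the authors stated that timing where they intended it. The mark in the safety column may be only a placeholder in a calendar with no progression column. Section 9 speaks of the samples as already collected at progression, and the Correlative Laboratory Manual, not available here, may give exact instructions. The aim is exploratory and conditional on funding.

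Most of this stands. A reader might infer that the sample is fixed at 30 days after the last dose; the documents do not support that, because 7.6 allows an earlier draw and footnote 12 does not mention the 30-day visit. A reader might also infer that palbociclib withdrawal alone invalidates the comparison. That fails on the plan's own schedule, since a draw at a scheduled scan is already 8 days after the last palbociclib dose and baseline is also before study drug. Nor is there any basis for assigning a contaminated share to the pairs.

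The defence does not remove the conflict of timing, the freedom to start other therapy before a calendar-compliant draw, or the lack of any rule in 9.1 for such samples.

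**Conclusion.** The point holds as one of conflicting timing and a missing analysis rule. A draw on the calendar's schedule falls 23–37 days after last study drug, which is about 15–36 days after a scheduled progression scan, and may follow the start of a new regimen. Section 9.1 would then present the change as a candidate mechanism of secondary resistance. The scan-to-visit range assumes progression found at a scheduled Day 1 scan and no further study drug after it.

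The number of affected samples is unknown and may be zero; with roughly a dozen pairs under the tamoxifen-rate assumption, even a few would matter. The conclusion reaches only the baseline-versus-progression comparison among responders. PFS, response and safety analyses do not depend on it. Low priority, but worth settling before the proteomic results are seen.

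**What to change.** In section 9.1 or the laboratory analysis plan:

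1. Make the main comparison among responders use only progression samples drawn before any new anti-cancer therapy. Identify them from the draw date, last-dose date and start date of the next regimen.
2. Capture new-therapy start dates for draws after day 30, which the general concomitant-medication rule does not cover.
3. Report samples drawn after new therapy separately.
4. Tabulate days from last palbociclib dose to draw. Describe this interval and do not model it: adjusting a whole proteome for it with about a dozen pairs would not be reliable.
5. Reconcile the calendar and section 7.6 with footnote 12, so that the draw is defined relative to documented progression.

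The cost is a few sentences and the use of dates that are largely recorded already. The downside is the loss of some pairs from a small exploratory analysis. If collection is complete, item 5 is mostly editorial, while items 1 to 4 can still be applied.
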